13.4 Analysis Plan

13.4.1 Analysis Populations.

Primary EHR data infant (PEDI) sample: All infants meeting inclusion/exclusion criteria for whom EHR data has been obtained at a 4-month or 6-month WCC in order to assess the primary endpoint of pediatric clinician adherence. Data regarding characteristics of the treating pediatric clinician are not required for an infant to be included in this population.

Secondary EHR data infant (SEDI) samples with pediatric clinician characteristics obtained: All infants meeting inclusion/exclusion criteria for whom EHR data has been obtained at a 4-month or 6-month WCC in order to assess the primary endpoint of pediatric clinician adherence and whose pediatric clinician has consented and completed the characteristics questionnaire information. In addition to characteristics obtained through the characteristics questionnaire information, data on completion of pre-study training for pediatric clinicians in the intervention arm will also be captured.

Exploratory EHR data infant (EEDI) samples

- With allergist adherence obtained (EEDI1): All high-risk infants meeting eligibility criteria who are referred to an allergist for testing and for whom data are obtained regarding the testing that was conducted, the outcome of the allergist testing and the recommendation provided by the allergist as to early introduction of peanut-containing food.
- With caregiver adherence obtained (EEDI2): All infants whose caregivers complete the FOABF and Caregiver Account of Clinician Peanut Recommendations, Testing and Introduction surveys at 12 and/or 24 months.

Pediatric clinician sample: All pediatric clinicians within the intervention group meeting consent and eligibility criteria who complete baseline and at least one follow-up knowledge, attitudes, or barriers and facilitators survey. Those clinicians in the control group will complete one follow-up knowledge, attitudes, or barriers and facilitators survey.

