Data for exploratory outcomes will be obtained through EHR data extraction and surveys of pediatric clinicians and the caregivers of infants seen for 4- or 6-month WCC. Pediatric clinicians in the intervention arm will be asked to provide informed consent and will complete three surveys over approximately 21 months. Pediatric clinicians in the control arm will be asked to provide informed consent following completion of data collection for the primary outcome and will complete one survey. Finally, caregivers, through the two surveys conducted at the time of their child's first and second birthdays, will provide information for exploratory outcomes.

Figure 3. iREACH Study Design

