8.1. Enrollment/Screening

Screening and enrollment of practice sites, pediatric clinicians, infants, and caregivers will largely take place by collecting data from practice managers or via the EHR pull. Pediatric clinicians and caregivers will provide consent prior to completing any surveys. We have received a waiver of informed consent and written signed

consent for the pediatric clinicians to complete surveys. We have also received a waiver of informed consent and signed consent for caregivers to complete surveys. However, for those caregivers that give permission to link their survey responses with their child's medical records, written signed consent will be obtained.

1. Practice sites will have completed legally-binding engagement agreements with Lurie Children's PPRG prior to study activation. These agreements will describe how EHR data will be accessed, copied, used, and transmitted for research. Once agreements are signed, practices will sign a study-specific Memorandum of Agreement (MOA), which summarizes study procedures and expectations. In addition to the MOA, practices will complete a practice characteristic questionnaire that will document that practice inclusion and exclusion criteria are met.
2. Pediatric clinicians within participating practices will be engaged in the study via practice managers and/or study practice champions once engagement agreements are executed and the Memorandum of Agreements are signed by practice representatives. Practice champions will complete a CRF form ensuring each clinician within participating practice fulfills inclusion/exclusion criteria. The study will be activated and practices are assigned to the respective randomization arms. Prior to survey administration, pediatric clinicians will provide informed consent.

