11.2. Participant Stopping Rules and Withdrawal Criteria

Practice Sites:

1. A practice site may elect to withdraw from current or future study activities.
2. The investigator, with the NIAID medical monitor's approval, can terminate a practice site if it fails to fulfill its obligations in accordance to the iREACH protocol.

Pediatric Clinicians:

1. A pediatric clinician may withdraw consent from participating in surveys.
2. When pediatric clinician leaves the practice for any reason they will be withdrawn from the study.
3. The investigator, with the NIAID medical monitor's approval, can terminate a pediatric clinician from participating in study activities if the investigator believes that further participation compromises the integrity of the study.

Infants:

1. Because infant data are obtained through the EHR and are only observational, no stopping rules nor withdrawal criteria apply.

Caregivers:

1. A caregiver may elect to withdraw consent from all future study activities; in such case, the caregiver will not be contacted by study staff for any future surveys or questionnaires.

2. A caregiver is “lost to follow-up” and assumed withdrawn after five attempts to reestablish contact by study representatives have failed.
3. A caregiver is withdrawn if they die.
4. The investigator may opt to withdraw a caregiver if they believe further participation compromises the integrity of the study.
5. A caregiver may elect to withdraw their “notice of privacy agreement” with the practice of which their child is a patient. If this occurs and the study team is notified, the child’s EHR data will be deleted from the EHR database.

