13.4.3 Supportive Analyses of the Primary Endpoint(s)

Consistent with the intent-to-treat principle, infants seen by all clinicians in each participating practice are included in the primary analysis (PEDI sample). Recognizing that some clinicians in treatment arm practices might decline to participate in the pre-study training and/or decline to utilize the CDS tool, we will also perform sensitivity analyses to investigate any change in these results that would be associated with excluding infants seen by each of these categories of non-participating clinicians: (1) declines training/uses CDS, (2) has training/declines CDS, (3) declines training and declines CDS.

The primary analysis will be repeated in the PEDI sample to evaluate the impact of missing data, clinician-level clustering, and type of pediatric clinician. Sensitivity analyses will be performed where 1) missing adherence data are not imputed and are left missing and 2) where missing data are imputed as being adherent. It is not possible to have missing data in the context of low-risk infants but is possible for high-risk infants. For high risk infants, adherence can be incomplete and data missing, if peanut-specific IgE is ordered for an infant but never conducted. Sensitivity analysis with a clinician-level random effect will also be performed to evaluate the impact of clinician-level clustering. Finally, sensitivity analysis will be conducted to assess any potential differences between types of pediatric clinicians (pediatricians and advanced practice nurses).

The primary analysis will be repeated in the PEDI sample combining all infants from both the high- and low-risk groups. Risk group and the interaction of risk group and intervention group will be included as fixed effects predictors.

The primary analysis will be performed again using the SEDI infant sample and adjusting for relevant covariates from the pediatric clinician questionnaire and practice site enrollment data. All questions in these forms and questionnaires will be explored one at a time for possible inclusion as covariates. Infants will be excluded from these analyses if information was not collected for each particular question.

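### Selection into the SEDI sample differs by arm, because the clinician questionnaire that defines it is given at the start in the intervention arm and at the end in the control arm

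*Combined protocol and SAP*

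**What the plan says.** Section 13.4.1 defines two infant samples that matter here. For PEDI, the primary sample, "Data regarding characteristics of the treating pediatric clinician are not required for an infant to be included in this population". SEDI keeps only infants "whose pediatric clinician has consented and completed the characteristics questionnaire information".

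Section 13.4.3 gives SEDI its purpose: "The primary analysis will be performed again using the SEDI infant sample and adjusting for relevant covariates from the pediatric clinician questionnaire" and from practice-level data gathered at enrolment. Missing items are handled by exclusion: "Infants will be excluded from these analyses if information was not collected for each particular question".

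Table 8.1 ties the characteristics questionnaire (age, sex, years in practice, professional type, patient volume) to consent. Consent comes at different times in the two arms. Table 8.5.1 puts consent and questionnaire at the beginning of the observation period for intervention clinicians and at the end for control clinicians. Section 3.2 agrees: "Pediatric clinicians in the control arm will be asked to provide informed consent following completion of data collection for the primary outcome".

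Section 11.2 deals with departures: "When pediatric clinician leaves the practice for any reason they will be withdrawn from the study".

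**The concern.** Membership of SEDI depends on something that happens after randomisation, namely whether the clinician was in post and answered when the questionnaire came round. That moment is about 18 months later in the control arm. Control clinicians who have left by then cannot qualify, whereas intervention clinicians who answered early and left later do.

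Two things are at stake. First, a difference between the SEDI and PEDI odds ratios would naturally be read as the effect of adjusting for clinician characteristics, but part of it could come from a different mix of clinicians in each arm. Second, patient volume is a covariate that can change over time. It would be recorded before exposure in one arm and after the observation period in the other.

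**Working it through.** **1. Trace each kind of clinician through the rules** (Sections 3.2, 8.3, 11.2 and 13.4.1).

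| Clinician | Intervention arm | Control arm |
|---|---|---|
| In post throughout | Asked at start; infants kept if answered | Asked at end; infants kept if answered |
| In post at start, leaves before end | Infants kept if answered before leaving | Not asked; infants lost |
| Hired during the study, in post at end | Timing of questionnaire not stated | Asked at end; infants kept if answered |
| Hired during the study, leaves before end | Timing of questionnaire not stated | Not asked; infants lost |

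Row 2 is the asymmetry that the text establishes. Rows 3 and 4 are open. Section 8.2.2 expects new hires and Section 4.3 excludes only those who start in the last three months, but Table 8.5.1 shows the intervention questionnaire at the beginning only.

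**2. The plan's own figures, as a yardstick.** The plan gives no figure for SEDI. Section 13.7 gives detectable differences in adherence of 18 points (high-risk) and 14 points (low-risk), from 30 practices (15 per arm), 17 and 333 infants per practice, within-cluster correlation 0.07, average adherence 0.50 and type 1 error 0.05. With design effect 1 + (m − 1) × 0.07 and effective n per arm = 15m / design effect, by normal approximation:
- High-risk: design effect 1 + 16 × 0.07 = 2.12; effective n = 255 / 2.12 = 120.3; power at 18 points 80.1%.
- Low-risk: design effect 1 + 332 × 0.07 = 24.24; effective n = 4,995 / 24.24 = 206.1; power at 14 points 81.4%.

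Both figures reproduce.

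**3. How many control infants could be lost.** The documents give no turnover rate, so annual turnover *a* is an assumption. Further assumptions are a constant departure hazard h = −ln(1 − a), posts refilled, visits spread evenly over 1.5 years, one clinician per infant, and full response from those asked. The share of control infants whose clinician has left by month 18 is

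f = 1 − (1 − e^(−1.5h)) / (1.5h).

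Example at a = 20%: 1.5h = 0.3347, e^(−0.3347) = 0.7155, f = 1 − 0.2845 / 0.3347 = 0.150.

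The counts take half of the 10,000 low-risk and 500 high-risk infants as controls. If leavers and stayers differ in adherence by d points, the control rate in SEDI moves by f × d.

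| Assumed annual turnover | Clinicians gone by month 18 | Control infants lost (f) | Of 5,000 low-risk | Of 250 high-risk | Shift, d = 10 | Shift, d = 30 |
|---|---|---|---|---|---|---|
| 5% | 7.4% | 3.8% | 188 | 9 | 0.4 | 1.1 |
| 10% | 14.6% | 7.5% | 375 | 19 | 0.8 | 2.3 |
| 15% | 21.6% | 11.3% | 563 | 28 | 1.1 | 3.4 |
| 20% | 28.4% | 15.0% | 751 | 38 | 1.5 | 4.5 |

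Shifts are in percentage points, and both values of d are assumptions. In the intervention arm this particular loss is near zero, provided the questionnaire is answered before departure.

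**4. The open case.** If intervention clinicians hired during the study are never asked, that arm loses joiners. Under the same assumptions (before applying the three-month hiring cutoff) the joiner share is about as large as the leaver share, because the model is symmetric in time. Equal numbers would not restore comparability, since one arm would lack joiners and the other leavers.

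**The case against.** The strongest reply is that this is a supportive analysis and the plausible effect is small. PEDI needs no clinician data, so the primary conclusion is untouched. With a 10-point difference between leavers and stayers, the control rate moves by 0.4 to 1.5 points, against detectable differences of 14 and 18. All of this stands and limits the weight of the point.

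Section 13.4.6 offers a partial check. It tabulates clinician disposition, including who consented, withdrew and saw infants throughout, and it compares infant baseline characteristics across samples. But it does not promise retention from PEDI to SEDI by arm, and a comparison of infant characteristics need not reveal selection on clinicians.

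Late contact with control clinicians can also be defended as avoiding a prompt about the guidelines. That is a reason to delay the knowledge and attitudes survey. It does not apply to age, sex, years in practice, professional type or patient volume.

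A reader might be tempted to go further in four ways that the documents do not support:
- **That only the control arm loses infants.** Non-response removes infants in either arm, intervention clinicians may leave before answering, and late intervention hires may never be asked.
- **That SEDI compares all starting clinicians with stayers.** Control SEDI also contains clinicians hired during the study who are still in post at the end.
- **That this is the only covariate-adjusted repeat of the primary analysis.** The primary model already includes practice volume, and Section 13.4.3 plans a combined model with risk group and its interaction with arm. SEDI is specific to clinician-questionnaire covariates.
- **That all the covariates are compromised by timing.** Sex is fixed, professional type usually is, and age and years in practice shift by a known interval. Patient volume is the real concern.

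**Conclusion.** The point holds in a limited form. Read together, Sections 3.2, 8.3, 11.2 and 13.4.1 make selection into SEDI differ by arm. Infants of control clinicians who leave before the end are excluded, while infants of intervention clinicians who answered and later left are retained. The adjusted SEDI estimate therefore cannot be set against the PEDI estimate as a pure effect of covariate adjustment, and patient volume does not mean the same thing in the two arms.

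The loss is about 4% to 15% of control infants if annual turnover is 5% to 20%, which is an assumed range. The bias itself has no computable size or direction, because the documents give neither a turnover rate nor adherence among leavers and stayers. Nothing here touches the primary analysis. The change is worth making because it is cheap and removes the asymmetry at its source.

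**What to change.** Record professional type, years in practice, age, sex and patient volume for every clinician in both arms, at practice activation or at hire. The vehicle exists in Section 8.1: "Practice champions will complete a CRF form ensuring each clinician within participating practice fulfills inclusion/exclusion criteria". Define SEDI by that record instead of by the survey, and state that clinicians hired during the study are recorded on joining. The control arm's knowledge and attitudes survey can stay at the end.

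In the analysis, report the number and share of PEDI infants retained in SEDI by arm. For each covariate, show the SEDI estimate without clinician covariates, on the same infants, beside the adjusted one. The step from PEDI to unadjusted SEDI then shows selection, and the step from unadjusted to adjusted SEDI shows adjustment. This reporting is useful even if the form is not changed.

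Do not try to equalise the arms by restricting both to clinicians still employed at the end. That conditions on a post-randomisation event and discards intervention data.

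The cost is a few added fields on an existing form, a reworded SEDI definition, some data entry by practice champions, and an IRB amendment, because clinician data would be recorded before the clinician's own survey consent.

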8.2.1.2. Caregivers

- Caregivers Characteristics Questionnaire (English and Spanish versions)
- Caregivers Feeding, Outcomes, Attitudes, Barriers and Facilitators to Guideline Implementation Questionnaire (FOABF) (English and Spanish versions)

Table 8.1 Data To Be Collected

| Topic | Data | When Collected |
|--|--|--|
| Pediatric Clinician Characteristics | Age, sex, years in practice, type of medical professional, patient volume | After informed consent |
| Pediatric Clinician Knowledge, Attitudes, Barriers, Facilitators to Guideline Implementation (KABF) | Knowledge of PPA Guidelines, attitudes towards guidelines, barriers and facilitators of guideline implementation | Intervention arm: After informed consent, mid-point of observation period & after 1° outcome data collection Control arm: after 1° outcome data collection |
| Caregiver Characteristics | Age, sex, ethnicity, education, income level, geographic location | After informed consent |

| | | |
|---|---|---|
| Caregiver Feeding, Outcomes, Attitudes, Barriers, Facilitators to Guideline Implementation (FOABF) | Peanut introduction practices, attitudes towards PPA Guidelines and barriers/facilitators of guideline implementation | After informed consent |
| Caregiver Report of Child's Adverse Reactions | Any reactions to peanut, and infant's allergy status | After informed consent and when infant is around 24 months old |
| Caregiver Account of Clinician Peanut Recommendations, Testing and Introduction | Information shared with caregiver by pediatric clinician regarding peanut introduction, allergy testing, and/or allergist referrals | After informed consent |
| Caregiver Stress, Quality of Life | Perceived stress and psychosocial outcomes | After informed consent and/or when infant is around 24 months old |
| Child Food Frequency Questionnaire | Detailed peanut and total diet food frequency questionnaire | After informed consent and/or when infant is around 24 months |

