8.3. Timeline for Study Activities

Study activities will begin with practice randomization and continue for 18 months of observation.

During the 18-month observation period, all infants that will be seen by pediatric clinicians in participant practices for at least one 4- or 6-month WCC will be considered eligible for EHR data extraction, as long as they (and their caregivers) fulfill inclusion/exclusion criteria. During this period, EHR data will be extracted as described above (Table 8.2). Additional study activities related to the pediatric clinicians that will take place during the same period are described in Table 8.5.1.

For each study infant, information will be obtained through EHR until age 30 months. In addition, activities related to the infant caregivers will take place at 11, 12 and 24 months of the infant's age, as described in Table 8.5.2.

| Table 8.5.1. Schedule of Activities-Practice Sites, Pediatric Clinicians | 18-Month Study Observation Period | | |
|---|--|---------------|------------|
| | Beginning | Middle | End |
| PRACTICES | | | |
| Randomization of Practice Sites | X | | |
| INTERVENTION ARM PEDIATRIC CLINICIANS | | | |
| Pediatric Clinician Informed Consent | X | | |
| Pediatric Clinician Characteristics Questionnaire | X | | |
| Pediatric Clinician Knowledge Attitudes Barriers Facilitators Survey #1 | X | | |
| Pediatric Clinician Knowledge Attitudes Barriers Facilitators Survey #2 | | | X |
| Pediatric Clinician Knowledge Attitudes Barriers Facilitators Survey #3 | | | X |
| CONTROL ARM PEDIATRIC CLINICIANS | | | |
| Obtain Pediatric Clinician Informed Consent | | | X |
| Pediatric Clinician Characteristics Questionnaire | | | X |
| Pediatric Clinician Knowledge Attitudes Barriers Facilitators Survey | | | X |

| Table 8.5.2. Schedule of Activities-Caregivers | Age of Infant | | |
|--|-------------------------|-------------------------|---|
| | Around 12-months | Around 24-months | |
| CAREGIVERS | | | |
| Caregiver Opt-out Letter (if needed based on recruitment method) | | X | |
| Caregiver Informed Consent and Consent to Link Survey with | | X | X |
| Caregiver Characteristics Questionnaire | | X | X |
| Caregiver Feeding, Outcomes Attitudes, Barriers, Facilitators | | X | X |
| Caregiver Account of Clinician Peanut Recommendations, Testing and Introduction Survey | | X | |
| Caregiver Stress, Quality of Life | | X | X |

| | | | |
|--|--|---|---|
| Infant Food Frequency Questionnaire | | X | X |
|--|--|---|---|

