Pediatric clinician knowledge of guidelines, attitudes towards implementation, and barriers and facilitators of adherence will be summarized in the pediatric clinician sample with descriptive statistics using pediatric clinicians as the unit of analysis. A proportion adherent summary statistic will be computed for each pediatric clinician and will be related to KABF with generalized linear mixed models as described in the primary endpoint analysis. The final pediatric clinician KABF assessed after primary outcome data collection will be compared between trial arms. Pediatric clinician KABF after primary outcome data collection in the control group will also be compared to the KABF of pediatric clinicians in the intervention arm at initial informed consent. Pediatric clinician KABF in the intervention arm at 6 months after informed consent and after primary outcome data collection will be separately analyzed for change over time. Any pediatric clinician who did not see infants for 4- or 6-month WCC during the 18-month observation period will be excluded from the analyses.

Caregiver survey data on feeding practices, reaction history, and barriers and facilitators to guideline implementation will be summarized in the EEDI2 sample with descriptive statistics using infants as the unit of analysis.

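### The between-arm comparison of the final clinician KABF survey requires a baseline survey in the intervention arm only; the time of survey #2 and the order of survey #1 and training also need settling.

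*Combined protocol and SAP*

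**What the plan says.** **Who enters the sample.** Section 13.4.1 takes eligible, consented intervention clinicians "who complete baseline and at least one follow-up knowledge, attitudes, or barriers and facilitators survey". It then says: "Those clinicians in the control group will complete one follow-up knowledge, attitudes, or barriers and facilitators survey". Section 3.2 explains the difference: control clinicians "will be asked to provide informed consent following completion of data collection for the primary outcome and will complete one survey", while intervention clinicians "will complete three surveys over approximately 21 months".

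**What is compared.** Section 13.4.5 names the pediatric clinician sample at the head of its KABF paragraph. It then plans three analyses:
- the final survey, intervention against control
- the control survey against the intervention survey taken at consent
- change over time within the intervention arm.

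The section labels these analyses exploratory.

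**When survey #2 is taken.** Table 8.1 gives "Intervention arm: After informed consent, mid-point of observation period & after 1° outcome data collection". Section 13.4.5 gives a different time: "Pediatric clinician KABF in the intervention arm at 6 months after informed consent and after primary outcome data collection will be separately analyzed for change".

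**When training happens.** Section 8.2.3 places it soon after enrollment. Section 13.4.3 allows that some intervention clinicians "might decline to participate in the pre-study training". Table 8.1 times survey #1 after consent, and Table 8.5.1 puts both at the beginning.

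**The concern.** A comparison of final surveys needs only a final survey from each clinician. Requiring survey #1 as well, in one arm only, means that two clinicians with the same response behaviour at the end are treated differently according to their practice's allocation. If intervention clinicians who skipped survey #1 differ in knowledge or attitudes from those who answered it, the intervention mean shifts for a reason unrelated to iREACH, and the control mean does not.

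Two smaller matters affect the other KABF analyses. The intermediate point of the change analysis has no single date. The survey used as baseline is also not explicitly placed before the training whose effect it would help to show. That order matters for change from baseline and for the comparison of controls with intervention clinicians at consent.

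**Working it through.** The plan states no sample size, power or expected response for the KABF analyses, so there is no figure to reproduce. The check sets the rules side by side and adds an illustration.

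**1. Entry to the final-survey comparison**

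| Clinician | Intervention arm | Control arm |
|---|---|---|
| Answers survey #1 and the final survey | kept | not applicable (no survey #1) |
| Answers the final survey only | dropped | kept |

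Inputs: about 200 clinicians in total (section 3.2). Results are given per 100 clinicians in an arm; an even split is an assumption, because practices and not clinicians are randomized 1:1. Let r be the response rate at each survey. The 86% is the response to the pilot's acceptability survey of 37 clinicians (section 1.4). The 60% is an assumed lower value.

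If responses to the two surveys are independent:
- Intervention clinicians usable in the comparison: r × r. At 86%, 0.86 × 0.86 = 0.74. At 60%, 0.60 × 0.60 = 0.36.
- Control clinicians usable: r, that is 0.86 or 0.60.
- Intervention final surveys discarded: r × (1 − r). At 86%, 0.86 × 0.14 = 0.12. At 60%, 0.60 × 0.40 = 0.24.

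So 12 to 24 per 100 are discarded. If the two responses have correlation ρ, the discarded share is r × (1 − r) × (1 − ρ). With ρ = 0.5 that is 6 to 12 per 100, and it tends to zero as ρ approaches 1.

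A count lost is not a bias. Under independence, the share of final responders without survey #1 is 1 − r. If their mean differs by d standard deviations from that of the others, the intervention mean shifts by (1 − r) × d. With d assumed at 0.2 to 0.5:
- at 86%: 0.14 × 0.2 = 0.03 to 0.14 × 0.5 = 0.07 SD
- at 60%: 0.40 × 0.2 = 0.08 to 0.40 × 0.5 = 0.20 SD.

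The documents give neither d nor its sign.

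**2. Time of survey #2**

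The mid-point of an 18-month observation period is 18 / 2 = month 9. For a clinician who consents at the start, the analysis plan puts the survey at month 6. The gap is 9 − 6 = 3 months. In the program-read text of Table 8.5.1, the row "Pediatric Clinician Knowledge Attitudes Barriers Facilitators Survey #2" has its mark in the end column, beside survey #3. That cell should be checked against the original PDF before any weight is put on it.

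**3. Order of survey #1 and training**

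Survey #1 follows consent. Training follows enrollment closely and is called pre-study in 13.4.1 and 13.4.3. No section says which comes first.

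**The case against.** The strongest reply is that KABF is an exploratory endpoint, and that the final survey falls at the same nominal time in both arms. A reader might infer from the differing entry rules that the KABF results cannot be interpreted. The documents do not support that: the final comparison depends neither on survey #2 nor on a baseline, and a change of entry rule repairs it.

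A reader might also infer that the rule favours iREACH by keeping the more engaged intervention clinicians. That is plausible but not shown. If engagement drives response, the same clinicians tend to answer both surveys and fewer are discarded. Nor does the rule necessarily select longer-serving clinicians. A later hire who consents and completes survey #1 and the final survey meets it, and in both arms clinicians who leave are withdrawn (section 11.2).

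A third inference is that survey #2 has three conflicting times. The third rests on one table cell, and the companion Table 8.5.2 has visibly shifted columns in the same text, so the cell may be a reading fault. Two conflicting times are firm.

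A fourth is that the baseline is taken after training. The order is unstated, and survey first is a natural reading, since 13.4.5 places this survey at initial consent. The module also carries its own knowledge tests before and after (section 6.1.1), so some of the knowledge gain is measured separately. The order of survey #1 and the module nevertheless remains unspecified.

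None of this answers the main point: the entry rule differs by arm for a comparison that does not need the difference.

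**Conclusion.** The point holds as a minor defect in an exploratory analysis. Followed literally, the sample definition drops intervention clinicians who completed the final survey without survey #1 and keeps the corresponding controls. The possible selection is of unknown size and direction. The 12 to 24 per 100 rests on assumed response rates, equal at each survey, and on independence; positive correlation lowers it. The shifts in SD units rest further on an assumed difference between responders and show only what order of size is possible.

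The survey #2 inconsistency is real between month 9 and 6 months after consent, and touches only the intermediate point of the within-arm change analysis. The order of survey #1 and training is a gap in the text, not a stated error. No primary or secondary conclusion depends on any of the three.

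**What to change.** 1. In 13.4.1 and 13.4.5, define the population for the between-arm final KABF comparison as every eligible clinician in either arm who completes the final survey. Require survey #1 only for the within-arm change analysis.
2. Choose one time for survey #2 and use it in Table 8.1, Table 8.5.1 and 13.4.5, after checking the Table 8.5.1 cell against the original PDF.
3. State that survey #1 precedes the training module, record both dates, and do not use as baseline any survey #1 dated after module completion.

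The cost is wording in the analysis plan and two tables, plus a date check. The final comparison and the change analysis will then have different denominators, which should be reported, and any survey #1 dated after module completion is lost to the change analysis. A common entry rule does not remove non-response to the final survey itself, so response by arm should be shown beside the comparison; section 13.4.6 already plans to summarize survey response.
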